9.4. Sample size

9.4.1. Calculation of sample size for vaccine efficacy study

The sample size required for phase III in vaccine efficacy study should meet the following requirements: ① For trial vaccine-1 or trial vaccine-2, the point estimation value of any vaccine efficacy is over 50%; ② the lower limit of 95% CI of any vaccine efficacy of trial vaccine-1 or trial vaccine-2 is no less than 30%.

Assume VEs of both vaccine-1 and vaccine-2 could reach 0.6. If 95% CI of any one of the two vaccines' efficacy is larger than 0.3, the vaccine will be considered to be successful. The statistical power achieves 90% when the number of COVID-19 cases in any one vaccine and placebo groups is 150. There are vaccine-1 and vaccine-2 groups in this trial. It will be analyzed when the number of COVID-19 cases in any one vaccine and placebo groups achieves 150.

The sample size required for each vaccine group was calculated by reference to document ^[15] according to the confirmed cases' cumulative number of COVID 19 epidemic situation in UAE and several other research sites since Jan. 2020 and the trend of newly diagnosed cases per day most recently, assuming the annual incidence rate of placebo group, P1 is 850/100,000, and the ratio of trial vaccine -1, trial vaccine -2 and placebo control group is 1:1:1.

$$N2=T/[(C+1- \pi 1) \times P1]=150/[(1+1-0.6) \times 0.0085]=12605 \text{ cases}$$

In the above formula, $\pi 1$ is the point estimation of VE, and C is the sample proportion of the test group and the control group.

If the drop-off rate is estimated as 15%, a total of $12605/(1-0.15) \times 3=44488$ cases were needed in the three groups. Considering the per capita distribution in the multi-center study site, 45,000 cases were planned and 15,000 cases in each group and the samples cases were allocated according to features of each site.

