
and the second interim analysis will be conducted, if the efficacy of the vaccine 1 reaches statistical criterion, i.e. the statistical test P value is less than 0.006 (corresponding to the efficacy of point estimates of more than 59%), which could suggest that the vaccine 1 satisfies the basic regulatory requirement on the efficacy of an inactivated SARS-CoV-2 vaccine.

When the total number of cases in the other vaccine group (such as vaccine 2) and the control group also reaches 100, the same statistical analysis will be carried out. If the statistical criteria are also met, it would also indicate that the efficacy of vaccine 2 has met with the basic requirements.

If one vaccine group or both vaccine groups could not reach statistical criteria at the second interim analysis, the cases will be continuously monitored until 150 cases across one of the vaccine groups (such as vaccine 1) and the control group are monitored by the DSMB and the final analysis will be conducted, if the efficacy of the vaccine 1 reaches statistical criterion, i.e. the statistical test P value is less than 0.023 (corresponding to the efficacy of point estimates of more than 50%), which could suggest that the vaccine 1 satisfies the basic regulatory requirement on the efficacy of an inactivated SARS-CoV-2 vaccine, otherwise, the efficacy of vaccine 1 will be considered as inconclusive.

When the total number of cases in the other vaccine group (such as vaccine 2) and the control group also reaches 150, the same statistical analysis will be carried out. If the statistical criteria are also met, it would also indicate that the efficacy of vaccine 2 has met with the basic requirements, otherwise, the efficacy of vaccine 2 will be considered as inconclusive.

If vaccine 1 (or vaccine 2) is conditionally approved for marketing authorization based on interim analysis data from a pivotal clinical efficacy trial, then the cases should be continuously monitored post-marketing authorization, until 150 cases are monitored across vaccine 1 (or vaccine 2) study group and control group in order to complete the clinical trial.

1. Introduction

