9.1. Hypothesis

Primary hypothesis:

In the healthy population who are older than 18 years, 95% confidence interval (CI) of vaccine efficacy (VE) after 14 days following two-dose vaccinations is larger than 30% in vaccine groups compared with placebo (point estimate of VE is achieves 50%).

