9.5 Interim analysis

Two interim analyses are planned in this trial when 1/3 and 2/3 of expected COVID-19 cases are observed. Early stopping for efficacy is considered in the interim analysis. Lan DeMets O'Brien-Fleming spending function is employed to control the family-wise type I error within 5% of two-sided. When the number of COVID-19 cases in any one vaccine (vaccine-1 or vaccine-2) and placebo groups achieves 50, the first interim analysis will be performed and the corresponding nominal significance level is $\alpha_1=0.0001$ (one-sided). When 100 COVID-19 cases in any one vaccine (vaccine-1 or vaccine-2) and placebo groups are observed, the second interim analysis will be conducted and the corresponding nominal significance level is $\alpha_2=0.0060$ (one-sided). If the null hypothesis is not rejected in the two interim analyses, the nominal significance level of final analysis is $\alpha_3=0.0231$ (one-sided). In the practical clinical trial, the nominal significance level will be calculated based on the number of COVID-19 cases observed at the interim analysis from pre-specified Lan DeMets O'Brien-Fleming spending function.

The interim analyses will be performed by DSMB.

Since CNBG's COVID-19 inactivated vaccine clinical trial project is following 1 (vaccine 1):1 (vaccine 2):1 (control) three-group settings, in order to ensure the integrity of the clinical trial, the research team cannot access to any information regarding the number of endpoint cases in either the vaccine group or the control group, therefore, the number of cases occurred in individual group can only be unblinded and monitored independently by the DSMB.

When the total number of cases in some vaccine group (such as vaccine 1) and the placebo group reaches 50, the DSMB will conduct the first interim analysis. If the vaccine's efficacy reaches statistical criterion in the first interim analysis, it could suggest that the corresponding vaccine satisfies the basic regulatory requirement on the efficacy of an inactivated SARS-CoV-2 vaccine.

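### Sections 9.1 and 9.4.1 judge final success by an ordinary 95% CI (one-sided 0.025), while 9.5 and the synopsis leave only one-sided 0.0231 for that analysis

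*Protocol*

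**What the plan says.** Two sets of passages govern the same final analysis at 150 cases in one vaccine group plus placebo.

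- **Protocol 9.1** puts the primary hypothesis as "95% confidence interval (CI) of vaccine efficacy (VE) after 14 days following two-dose vaccinations is larger than 30% in vaccine groups compared with placebo", with a VE point estimate that reaches 50%.
- **Protocol 9.4.1** states: "If 95% CI of any one of the two vaccines' efficacy is larger than 0.3, the vaccine will be considered to be successful". It also requires that "the point estimation value of any vaccine efficacy is over 50" per cent. On power it says: "The statistical power achieves 90% when the number of COVID-19 cases in any one vaccine and placebo groups is 150".
- **Protocol 9.5** plans efficacy looks at 50 and 100 cases with a Lan-DeMets O'Brien-Fleming function, two-sided 5% overall, and one-sided nominal levels of 0.0001 and 0.0060. For the last look it says: "If the null hypothesis is not rejected in the two interim analyses, the nominal significance level of final analysis is" one-sided 0.0231. The levels are to be recalculated from the case counts actually observed. A vaccine that misses the final criterion is inconclusive.
- **The synopsis (interim analyses)** gives the final criterion as "the statistical test P value is less than 0.023 (corresponding to the efficacy of point estimates of more than 50" per cent.

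No passage says that the 95% CI in 9.1 and 9.4.1 is adjusted for the interims, or which rule prevails.

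**The concern.** A lower 95% confidence limit above 30% is equivalent to rejecting VE ≤ 30% at one-sided 0.025. The group-sequential plan in 9.5 no longer has 0.025 to give at the final look, because some of it has been spent at 50 and 100 cases. The protocol therefore holds two thresholds for one decision. A final one-sided p-value between 0.0231 and 0.025 is a success under 9.1 and 9.4.1 (if the point-estimate condition is also met) and inconclusive under 9.5. If the 9.1/9.4.1 rule is the one applied, the overall error exceeds the limit that 9.5 sets. This is the primary success rule of a trial meant to support marketing authorisation, so it should have one reading only.

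**Working it through.** **Inputs.** Null VE 30%, assumed VE 60%, 150 cases, 1:1 within each vaccine-placebo pair (9.1, 9.4.1). Looks at 50, 100 and 150 cases, so information fractions t = 1/3, 2/3, 1, with nominal levels 0.0001, 0.0060, 0.0231 (9.5). Person-year rates compared by Poisson regression (9.3). The interval method is not fixed in the protocol, so several tests are shown.

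**1. The levels in 9.5 reproduce.** The spending function is α(t) = 2 − 2Φ(z/√t) with z = 2.2414, the upper 0.0125 point. Cumulative spend is 0.000104, 0.00605 and 0.0250. Solving for the nominal one-sided levels gives 0.00010, 0.0060 and 0.0231, as stated.

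**2. Equivalent interval.** 1 − 2 × 0.0231 = 0.9538, so 9.5 implies a 95.38% CI at the final look (critical value 1.994, against 1.960 for 95%).

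**3. Overall error for one vaccine-placebo comparison.** This is the probability of crossing at any look, from a trivariate normal with correlations √(tᵢ/tⱼ).

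| Final-look rule | One-sided error | Two-sided |
|---|---|---|
| 0.0231 (9.5) | 0.0250 | 5.0% |
| Ordinary 95% CI (9.1, 9.4.1) | 0.0268 | 5.35% |

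(0.02676 × 2 = 0.0535.) Both rows use 0.0001 and 0.0060 at the interims.

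**4. Where the two rules disagree.** Wald test: z = [ln(RR) − ln 0.7] / √(1/x + 1/y), where x and y are vaccine and placebo cases and RR is the ratio of person-year rates.

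| Cases, vaccine v placebo | Person-time | VE | One-sided p | 95% limit | 95.38% limit | Result |
|---|---|---|---|---|---|---|
| 49 v 101 | equal | 51.5% | 0.0176 | 31.8% | 31.4% | succeeds on both |
| 50 v 100 | equal | 50.0% | 0.0260 | 29.8% | 29.4% | fails on both |
| 50 v 100 | vaccine +0.5% | 50.2% | 0.0243 | 30.1% | 29.7% | split |
| 49 v 99 | equal | 50.5% | 0.0236 | 30.3% | 29.9% | split |

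The 49 v 99 row (148 cases) holds the final level at 0.0231 for illustration. At exactly 150 cases with equal person-time, exact and score tests give the same cut-off as Wald. For 49 vaccine cases the p-values are 0.0200 (exact) and 0.0171 (score). For 50 they are 0.0298 and 0.0255. On a continuous scale at 150 cases the disputed band is VE of about 50.2% to 50.5% (Wald) or 50.1% to 50.4% (score).

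**5. Power.** Given 150 cases, the vaccine share is p0 = 0.7/1.7 = 0.4118 under the null and p1 = 0.4/1.4 = 0.2857 under VE 60%. The standard deviations are s0 = 0.4922 and s1 = 0.4518. Power = Φ{[(p0 − p1)√150 − z·s0] / s1}.

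- At 0.025: (1.5438 − 1.9600 × 0.4922) / 0.4518 = 1.282, giving 90.0%, the stated figure.
- At 0.0231: (1.5438 − 1.9936 × 0.4922) / 0.4518 = 1.245, giving 89.4% for the final look. The whole three-look design gives 89.5%.

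**The case against.** The strongest defence is that 9.5 is plainly the operative rule. It fixes the function, the looks, the levels and their recalculation, and the synopsis repeats the final threshold as a p-value. On this view 9.1 only names the null and the overall 5%, and the numbered requirements in 9.4.1 are inputs to the sample size. Stating a hypothesis with a 95% CI and then allocating its 5% across looks is common practice, and details of interval coverage are often left to the SAP. Much of this stands, and a careful reader would probably follow 9.5. But 9.4.1 goes beyond a design input. It says when a vaccine will be considered successful, and nothing there points to 9.5. Two stated thresholds for one decision are a conflict within the protocol, not a detail awaiting the SAP.

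It is also fair to object that the verdict seldom changes. That is right: the band is about 0.3 VE points wide, or one case at some totals near 150.

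Three stronger readings are tempting and should not be drawn:

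- **A reader might infer that the 95% CI rule could be used to declare success at an interim.** The documents do not support this. The synopsis and 9.5 set explicit interim levels of 0.0001 and 0.0060, and 9.4.1 ties its analysis to 150 cases.
- **A reader might infer that the 90% power is wrong.** A drop from 90.0% to 89.4% is smaller than the spread between test choices at 0.025 (87.2% for a Wald test, 92.9% for a Schoenfeld-type formula).
- **A reader might infer that any borderline result at 150 cases would split.** With equal person-time it does not under exact, Wald or score tests. Likelihood-ratio (p = 0.0241) and mid-p (p = 0.0249) versions do fall between the levels at 50 v 100, but VE is then exactly 50% and fails the over-50% condition in 9.4.1.

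**Conclusion.** The point holds as an inconsistency in the final success criterion. Sections 9.1 and 9.4.1 imply one-sided 0.025. Section 9.5 and the synopsis imply 0.0231. Following the former after the two planned looks gives 5.35% two-sided error per vaccine-placebo comparison instead of 5%. The excess is small and the zone of disagreement is narrow, but it lies at a VE of about 50%, where the protocol also sets its point-estimate requirement. The error figures assume looks at exactly 50, 100 and 150 cases and normal theory. The borderline examples depend on the test, which the protocol does not fix. The sample size is not affected.

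**What to change.** In 9.1 and 9.4.1, state that the CI used to declare success is at the Lan-DeMets level of 9.5 for the look concerned: about 95.4% at the final analysis, recalculated from the actual case counts as 9.5 already provides. Add that the ordinary 95% CI is reported descriptively. In 9.4.1, note the alpha level behind the power figure (90.0% at one-sided 0.025, about 89.4% at 0.0231) and keep 150 cases.

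The cost is a few sentences of protocol text and a final criterion that is very slightly stricter than the one now written in 9.1 and 9.4.1.

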9.4.2. Estimation of Sample size for Immunogenicity Study

The estimation of sample size should meet the needs of immunogenicity hypothesis analysis.

(1) Superiority test based on seroconversion rate of antibody after immunization

Referring to the relevant data of Phase I and Phase II clinical trials of this product (the current data are all hypotheses and will be revised later according to the results of Phase I and Phase II clinical trials), the 4-fold growth rate of IgG antibody in placebo group is 10%, the actual difference D1 of the 4-fold growth rate of IgG antibody in test group and control group is 0.30, and the superiority margin $\delta = 0.20$). The hypothesis can only be considered as valid when four-fold growth rate of antibody and GMT both reach the superiority. In order to control the probability of overall type I

error, the probability of type I error ($= 0.025/2=0.0125$ (One-sided) at each superiority comparison; power 0.90; z test is used for the calculation of test statistic, designed as ratio of 1: 1. It is calculated about 445 cases for each group, and 900 cases for each test group according to the estimation of 50% dropouts.

Table 5. Sample Size Required for Antibody Seroconversion rate Superiority test under Different Parameters

Probability level (one-sided)	Superiority Margin	Control rate p2	Rate difference Δ_1	Power $1 - \beta$	Calculate sample size per group	Consider the sample size after 50% dropouts
0.0125	0.20	0.05	0.30	0.90	377	760
0.0125	0.20	0.10	0.30	0.90	445	900

(2) GMT superiority test based on antibody post-immunization

Referring to the relevant data of Phase I and Phase II clinical trials of this product (the current data are all hypotheses and will be revised later according to the results of Phase I and Phase II clinical trials), the standard deviation of antibody titer is set to be about 0.50 (logarithmic scale). The hypothesis can only be considered as valid when the antibody seroconversion rate and GMT both meet superiority. In order to control the probability of overall type I error, the probability of type I error ($= 0.025/2 = 0.0125$ (one-sided) at each superiority comparison; power is 0.90; The Superiority margin = 0.079 (logarithmic scale, i.e. GMT test group/GMT control group ≥ 1.2 after immunization); The difference D between the average antibody titres (logarithmic scale) of the test group and the control group is 0.20. The standard deviation is 0.5; The experimental group and the control group is designed at a ratio of 1: 1. It is calculated about 425 cases for each group, and 850 cases for each group according to the estimation of 50% dropouts.

Table 6. Sample Size Required for Antibody GMT Superiority Test under Different Parameters

Probability level (One-sided)	Standard deviation (logarithmic scale)	Superiority Margin (Logarithmic Scale)	Mean difference (logarithmic scale)	Power $1 - \beta$	Calculate each group Sample size	Estimated sample size after 50% dropouts
0.0125	0.50	0.041 (ratio 1.1)	0.20	0.90	247	500
0.0125	0.50	0.079 (ratio 1.2)	0.20	0.90	425	850

According to the principle of maximizing the sample size, taking into account the factors of dropouts and the distribution of the number of subjects on the multi-center research site.

9.5 Interim analysis

Two interim analyses are planned in this trial when 1/3 and 2/3 of expected COVID-19 cases are observed. Early stopping for efficacy is considered in the interim analysis. Lan DeMets O'Brien-Fleming spending function is employed to control the family-wise type I error within 5% of two-sided. When the number of COVID-19 cases in any one vaccine (vaccine-1 or vaccine-2) and placebo groups achieves 50, the first interim analysis will be performed and the corresponding nominal significance level is $\alpha_1=0.0001$ (one-sided). When 100 COVID-19 cases in any one vaccine (vaccine-1 or vaccine-2) and placebo groups are observed, the second interim analysis will be conducted and the corresponding nominal significance level is $\alpha_2=0.0060$ (one-sided). If the null hypothesis is not rejected in the two interim analyses, the nominal significance level of final analysis is $\alpha_3=0.0231$ (one-sided). In the practical clinical trial, the nominal significance level will be calculated based on the number of COVID-19 cases observed at the interim analysis from pre-specified Lan DeMets O'Brien-Fleming spending function.

The interim analyses will be performed by DSMB.

Since CNBG's COVID-19 inactivated vaccine clinical trial project is following 1 (vaccine 1):1 (vaccine 2):1 (control) three-group settings, in order to ensure the integrity of the clinical trial, the research team cannot access to any information regarding the number of endpoint cases in either the vaccine group or the control group, therefore, the number of cases occurred in individual group can only be unblinded and monitored independently by the DSMB.

When the total number of cases in some vaccine group (such as vaccine 1) and the placebo group reaches 50, the DSMB will conduct the first interim analysis. If the vaccine's efficacy reaches statistical criterion in the first interim analysis, it could suggest that the corresponding vaccine satisfies the basic regulatory requirement on the efficacy of an inactivated SARS-CoV-2 vaccine.

If some vaccine group could not reach statistical criteria at the first interim analysis, the cases will be continuously monitored until 100 cases between the vaccine group and placebo group, and the second interim analysis will be activated accordingly. If the vaccine's efficacy reaches statistical criterion in the second interim analysis, it could suggest that the corresponding vaccine satisfies the basic regulatory requirement on the efficacy of an inactivated SARS-CoV-2 vaccine.

If some vaccine group could not reach statistical criteria in the two interim analyses, the cases will be continuously monitored until 150 cases, and the final analysis will be conducted, if the

vaccine's efficacy reaches statistical criterion, it could suggest that the corresponding vaccine satisfies the basic regulatory requirement on the efficacy of an inactivated SARS-CoV-2 vaccine, otherwise, the efficacy will be considered as inconclusive.

If vaccine 1 (or vaccine 2) is conditionally approved for marketing authorization based on interim analysis data from a pivotal clinical efficacy trial, then the cases should be continuously monitored post-marketing authorization, until 150 cases are monitored across vaccine 1 (or vaccine 2) study group and placebo group in order to complete the clinical trial.

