
The interim analyses
	
Two interim analyses are planned in this trial when 1/3 and 2/3 of expected COVID-19 cases are observed. Early stopping for efficacy is considered in the interim analysis. Lan DeMets O'Brien-Fleming spending function is employed to control the family-wise type I error within 5% of two-sided. When the number of COVID-19 cases in any one vaccine (vaccine-1 or vaccine-2) and placebo groups achieves 50, the first interim analysis will be performed and the corresponding nominal significance level is $\alpha_1=0.0001$ (one-sided). When 100 COVID-19 cases in any one vaccine (vaccine-1 or vaccine-2) and placebo groups are observed, the second interim analysis will be conducted and the corresponding nominal significance level is $\alpha_2=0.0060$ (one-sided). If the null hypothesis is not rejected in the two interim analyses, the nominal significance level of final analysis is $\alpha_3=0.0231$ (one-sided). In the practical clinical trial, the nominal significance level will be calculated based on the number of COVID-19 cases observed at the interim analysis from pre-specified Lan DeMets O'Brien-Fleming spending function.
 
The interim analyses will be performed by DSMB.
 
Since CNBG's COVID-19 inactivated vaccine clinical trial project is following 1 (vaccine 1):1 (vaccine 2):1 (control) three-group settings, in order to ensure the integrity of the clinical trial, the research team cannot access to any information regarding the number of endpoint cases in either the vaccine group or the control group, therefore, the number of cases occurred in individual group can only be unblinded and monitored independently by the DSMB.
 
When the total number of cases in one of the vaccine group (such as vaccine 1) and the control group reaches 50, the DSMB will conduct the first interim analysis, if the efficacy of the vaccine 1 reaches statistical criterion, i.e. the statistical test P value is less than 0.0001 (corresponding to the efficacy of point estimates of more than 76%), which could suggest that the vaccine 1 satisfies the basic regulatory requirement on the efficacy of a inactivated SARS-CoV-2 vaccine.
 
When the total number of cases in the other vaccine group (such as vaccine 2) and the control group also reaches 50, at which time, the same statistical test will be carried out. If the statistical criteria are also met, it would also indicate that the efficacy of vaccine 2 has met with the basic requirements.
 
If one vaccine group or both vaccine groups could not reach statistical criteria at the first interim analysis, the cases will be continuously monitored until 100 cases across one of the vaccine groups (such as vaccine 1) and the control group are monitored by the DSMB

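### The family-wise 5% claim in Section 9.5 holds for each vaccine over its three looks, not across the two vaccines; with both at the 30% null, the chance of at least one false success is about 4.0% to 4.7% one-sided

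*Protocol*

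**What the plan says.** Protocol Section 9.5 sets the timing of the looks: "Two interim analyses are planned in this trial when 1/3 and 2/3 of expected COVID-19 cases are observed". It then says that the "spending function is employed to control the family-wise type I error within 5% of two-sided". The Synopsis (The interim analyses) makes the same claim.

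The one-sided nominal levels follow directly: 0.0001 at 50 cases, 0.0060 at 100 and 0.0231 at 150. Cases are counted within a vaccine-placebo pair, so the first look is triggered as follows: "When the number of COVID-19 cases in any one vaccine (vaccine-1 or vaccine-2) and placebo groups achieves 50".

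The Synopsis takes the second vaccine through its own count of 50 cases with placebo, "at which time, the same statistical test will be carried out", and repeats the arrangement at 100 and 150. Section 9.5 draws a separate conclusion for each vaccine. Section 9.4.1 states the success rule for whichever vaccine has a 95% interval that "is larger than 0.3, the vaccine will be considered to be successful".

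Allocation is 1:1:1 with one placebo group. The protocol does not split alpha, order the vaccines or otherwise adjust across the two efficacy comparisons. It does halve alpha elsewhere: Section 9.4.2 uses 0.0125 for each of the two immunogenicity tests.

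**The concern.** A spending function distributes error over repeated looks at one comparison. It does nothing about a second comparison tested in parallel. In a trial of two vaccines, a reader will take family-wise control to cover both.

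The plan links crossing a boundary to meeting the basic regulatory requirement on efficacy, and it foresees conditional marketing authorization on interim data. A regulator or DSMB member relying on the stated figure would understate the chance that the trial wrongly passes at least one vaccine.

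**Working it through.** **Inputs (Protocol 9.4.1 and 9.5).** Information fractions 1/3, 2/3 and 1. Levels 0.0001/0.0060/0.0231 one-sided. Null efficacy 30%, alternative 60%. 150 cases per pair, 1:1:1 allocation. Five per cent two-sided means 2.5% one-sided in the efficacy direction.

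**1. What the printed levels spend.** The O'Brien-Fleming-type function is α(t) = 2[1 − Φ(z₁₋α/₂/√t)]. Solving the boundaries gives:

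| One-sided alpha for one comparison | 50 cases | 100 cases | 150 cases |
|---|---|---|---|
| 0.025 | 0.00010 | 0.00601 | 0.02313 |
| 0.0125 | 0.00002 | 0.0022 | 0.0118 |
| Protocol | 0.0001 | 0.0060 | 0.0231 |

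The protocol's levels match 0.025 on a single comparison and do not match a halved alpha.

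**2. The sizing uses the same alpha.** Given a case in the pair, the chance that it is a vaccine case is p₀ = 0.7/1.7 = 0.412 at the null and p₁ = 0.4/1.4 = 0.286 at 60%. The single-look normal approximation is

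Φ{[√150(p₀ − p₁) − 1.96√(p₀(1 − p₀))]/√(p₁(1 − p₁))} = 90.0%.

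This reproduces the stated 90%, again with the full 0.025 for one vaccine.

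**3. Correlation from the shared placebo arm.** For log rate ratios the correlation is (1/c_P)/(1/c_V + 1/c_P) = c_V/(c_V + c_P), where c_V and c_P are the vaccine and placebo case counts. With both vaccines at 30% this is 0.7/1.7 = 0.41. It would be 0.5 if case rates were equal in all arms.

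**4. Chance of at least one false success, normal theory.** For one look this is 1 − Φ₂(1.96, 1.96; ρ). For three looks it is one minus the probability that neither vaccine crosses, from a six-dimensional normal (two vaccines, three looks).

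| ρ | One look | Three looks |
|---|---|---|
| 0.41 (both at 30%) | 4.65% | 4.66% |
| 0.50 | 4.54% | 4.54% |
| 0 (upper reference, 1 − 0.975²) | 4.94% | 4.94% |

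**5. Simulated case counts.** Cases were drawn in the ratio 0.7:0.7:1 (both vaccines at 30%, equal person-time assumed), and each pair was tested at its own 50, 100 and 150 cases. There were 400,000 runs per rule.

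| Test rule | Per vaccine | At least one |
|---|---|---|
| Exact binomial at the stated levels | 2.2% | 4.1% |
| Wald at the stated levels | 2.1% | 4.0% |
| Score at the stated levels | 2.1% | 4.0% |
| Synopsis efficacy thresholds 76%/59%/50% | 2.3% | 4.4% |

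A further 200,000-run exact simulation gave 2.1% per vaccine and 4.0% for at least one. A log rate ratio test using the null standard error gave 6.0%, but its per-vaccine error is already about 3.2%. That excess belongs partly to the approximation, so the figure is left out of the range.

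**6. Does the required 50% point estimate help?** No. The exact final test rejects at 49 or fewer vaccine cases out of 150, where the estimate is 1 − 49/101 = 51.5%, already above 50%.

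**The case against.** **The family may be the looks.** The grammatical subject of the sentence is the spending function, in a section on interim analysis, and the three levels follow at once. Read as the family of looks within one comparison, the statement is true. This stands as a reading, and it is why no boundary is called wrong. It does not make the wording right, because in a two-vaccine trial the term covers both comparisons unless the text says otherwise.

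**Each vaccine is judged on its own.** A reader might infer from Section 9.4.1 that the trial succeeds if either vaccine does. The documents do not support that. The rule there declares the particular vaccine successful, Section 9.5 concludes for the corresponding vaccine, and each pair runs to its own 150 cases. The products differ in strain, manufacturer and specification. Whether distinct products sharing a control need adjustment is debatable, and leaving them unadjusted is defensible. But a plan that does so should claim per-vaccine control.

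**The excess is a worst case.** This also stands. With the exact test, the false-success rate is 2.2% with one vaccine at 30% and the other at 60%, 2.4% with true efficacies of 20% and 30%, and 0.5% with both at 20% (100,000 runs). It would be wrong to say that the error is always nearly doubled.

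**The SAP may deal with it.** The protocol itself fixes the levels. It allows recalculation only for the observed case numbers from the same spending function, which is not an adjustment across vaccines.

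**Conclusion.** The stated operating characteristic is wrong as a claim about the two vaccines together. Error over the three looks is controlled at 2.5% one-sided for each vaccine. Across the two, with both true efficacies at 30%, the chance of at least one false success is about 4.0% (exact test) to 4.7% (normal approximation), that is 1.6 to 1.9 times 2.5%. The figure rests on equal follow-up in the arms, a shared placebo group with correlation 0.41 to 0.5, and the test used.

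Two stronger inferences are not supported. The per-vaccine boundaries and case counts are not shown to be wrong. Nor does a quick Dunnett repair follow: a common level of 0.0135 with power of about 85% rests on correlation 0.5, whereas 0.41 applies at the null and calls for about 0.0132. The 85% is also a single-look figure, not the power of the three-look design.

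**What to change.** In Section 9.5 and in the Synopsis, replace the family-wise sentence with a statement that:

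- type I error is controlled at 2.5% one-sided (5% two-sided) over the three looks for each vaccine separately;
- no adjustment is made across the two vaccines;
- the chance of at least one false success is about 4.0% to 4.7% one-sided when both vaccines have a true efficacy of 30%.

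This costs one sentence in each place and a less favourable figure. No boundary, case count or trial procedure changes.

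If control across both vaccines is really intended, the alpha must be split and the nominal levels and three-look power recalculated, with more cases if 90% power is to be kept. As an indication, a Bonferroni split at 0.0125 gives levels of about 0.00002/0.0022/0.0118 and a chance of at least one false success of 2.3% to 2.4% by normal theory. Single-look power at 150 cases falls from 90.0% to 83.5% by the approximation that reproduces the protocol's figure, or from 88.4% to 80.0% by the exact test. These single-look values show the size of the loss and do not replace the three-look calculation.
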